12. STATISTICAL CONSIDERATIONS

12.1. Sample Size

All patients who complete the basic protocol SD-003 and who wish to receive SD-101 (containing 6% allantoin) will be eligible to enter this open label extension.

12.2. Study Populations

Study populations are the same as defined for SD-003.

12.3. Analysis Considerations

This study is an open label extension of SD-003 and will include those patients completing that protocol and wishing to receive SD-101 (containing 6% allantoin). In general, results will be summarized using descriptive statistics. Additional evaluations may be made to compare responses of patients in this extension study with their responses in SD-003.

13. END OF THE STUDY

The end of the study will be defined as the last patient's last visit.

The study will be terminated early if, in the opinion of the Sponsor, Investigators, or IRBs/ECs, an unacceptable risk to the safety and welfare of subjects is posed by the continuation of the study in light of review of the key unexpected adverse events occurring during the trial.

Within the provisions of informed consent / assent and good clinical judgment with respect to safety, every attempt will be made to have subjects complete the study.

The following reasons are grounds to terminate a subject's participation in the study:

1. Subject develops intolerable adverse effects, including but not limited to:
 - Severe and widespread dermatological reactions beyond the area of application.
 - Severe local reactions requiring systemic steroid therapy.
2. Any subject who becomes significantly noncompliant with study drug administration, study procedures, or study requirements should be withdrawn from study treatment when the circumstances increase risk to the subject or substantially compromise the interpretation of study results.
3. The subject's health would be jeopardized by continued participation.

4. Investigator judgment deems it appropriate.
5. The subject wishes to withdraw for any reason.
6. The Sponsor elects to end the study, or any portion thereof, for any reason.
7. If SD-101 becomes commercially available, the Sponsor may transition subjects to commercial drug supply.

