8.4. Withdrawal Criteria/Study Discontinuation

Subjects may withdraw from the study at any time without stating a reason and without prejudice to further treatment. The Investigator may withdraw a subject from the study and discontinue study treatment and assessments at any time due to safety concerns. Full skin examination will be performed at each scheduled study center visit. If SD-101 causes any significant rash that has not occurred previously in the subject, the Investigator should consider discontinuing the subject. In addition, if lesions appear to significantly worsen above the normal cycle seen in the patient, with use of SD-101, the Investigator should consider discontinuing the subject.

Early discontinuation of any subject who has given informed consent / assent to participate will be recorded including the reason for discontinuation. The primary reason for a subject withdrawing prematurely will be selected from the following standard categories of early discontinuations.

1. Adverse Event (Adverse Reaction): Clinical events occurred that are reported that in the medical judgment of the Investigator are grounds for discontinuation in the best interests of the subject.
2. Withdrawal of Consent: The subject desired to withdraw from further participation in the study. The subject is not obligated to provide any reason for withdrawal of consent, but where a reason is given this will be recorded on the eCRF.
3. Protocol Violation: The subject failed to adhere to the protocol requirements, at the Investigator's discretion.

4. Lost to Follow-Up: The subject stopped coming for visits and study personnel were unable to contact the subject.
5. Other: The subject was terminated for a reason other than those listed above, such as, termination of study by Sponsor.

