10. STUDY MEDICATION AND ADMINISTRATION

10.1. Study Medication and Administration

The SD-101 cream (containing 6% allantoin) concentrations will be supplied in 8 ounce tubes, to be reclosed after use and stored at room temperature.

SD-101 dermal cream (containing 6% allantoin) will be applied once a day to the entire body for the duration of the study.

The study cream will be returned during each study center visit to evaluate compliance. Any unused study medication will be re-dispensed to the patient at each visit.

Additional information on the composition of the SD-101 dermal cream is contained in the SD-101 Investigator's Brochure.

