10.2. Selection of Doses in the Study

SD-101 dermal cream (containing 6% allantoin) will be applied topically once a day to the entire body.

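### Does whole-body application make the named skin-reaction ground for ending participation unusable?

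*Protocol*

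**What the plan says.** Section 13 of the protocol (End of the Study) gives seven grounds for ending a subject's participation. Ground 1 opens with "Subject develops intolerable adverse effects, including but not limited to" and then gives two examples:

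- "Severe and widespread dermatological reactions beyond the area of application"
- "Severe local reactions requiring systemic steroid therapy"

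Ground 3 in the same list reads "The subject's health would be jeopardized by continued participation", and ground 4 is the investigator's own judgment.

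The area of application is stated consistently. Section 10.1 says that the cream "will be applied once a day to the entire body for the duration of the study". Section 10.2 repeats it: "SD-101 dermal cream (containing 6% allantoin) will be applied topically once a day to the entire body". The synopsis and Section 9.3 agree.

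Section 8.4 deals with withdrawal separately. It lets the investigator withdraw a subject whenever there is a safety concern and requires a full skin examination at each scheduled center visit. It also says: "If SD-101 causes any significant rash that has not occurred previously in the subject, the Investigator should consider discontinuing the subject". A parallel sentence covers lesions that worsen clearly beyond the patient's usual cycle.

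**The concern.** The first example under ground 1 turns on where the reaction lies: it must extend past the treated skin. If the whole body is treated, 100% − 100% = 0% of the skin is left for it to extend to. The example most relevant to a whole-body cream would then be empty.

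Section 8.4 appears to make matters worse. It uses a milder trigger, a significant new rash, with a softer action, and neither section refers to the other on this point. A reader could conclude that investigators at the seven centers hold two different thresholds for one event, and that whether a skin reaction ends treatment depends on which section a center follows.

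If that were so, the stake would be real. The primary objective is continued safety, tolerability at the application sites is among the named safety assessments, and up to 48 subjects may be treated for years. A stop that cannot operate, or that operates differently by center, would affect both the subjects and the reading of the safety data.

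**Working it through.** No arithmetic bears on this point. The protocol attaches no rate, sample size, power or alpha to the criterion, so there is no figure to reproduce. The check sets the passages side by side.

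**Step 1: is the example empty as worded?** Section 13 asks for a reaction outside the treated area, and Sections 10.1 and 10.2 make the treated area the entire body. Used as directed, the cream leaves no skin outside it, so the example has no workable meaning read literally. The one exception is a subject who leaves some skin untreated in practice, which is conceivable because ground 2 of Section 13 anticipates noncompliance with study drug administration. The mismatch is real.

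**Step 2: is ground 1 empty as well?** No. What ground 1 requires is intolerable adverse effects. The two sub-bullets illustrate it, and the introductory words make the list open. A severe, widespread reaction on treated skin that the subject cannot tolerate meets ground 1 without matching either example.

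**Step 3: what other routes reach a severe skin reaction on treated skin?**

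- Section 13, ground 1, second example: severe local reactions that need systemic steroids. It is not limited to skin outside the treated area.
- Section 13, ground 3: health at risk from continuing. No location condition.
- Section 13, ground 4: investigator judgment. No condition at all.
- Section 8.4: withdrawal at any time over safety concerns. No location condition.
- Section 8.4: significant new rash, or lesions worsening beyond the usual cycle. No location condition.

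With ground 1 itself, that makes six routes. Removing the faulty example closes none of them.

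**Step 4: do Sections 8.4 and 13 conflict?** Section 8.4 asks the investigator to consider discontinuing at a significant new rash. Section 13 lists intolerable effects as grounds for termination. These are two levels of severity with two strengths of action, and both leave the decision with the investigator. Neither forbids what the other permits. They are graded, not contradictory.

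**Step 5: does any result depend on the example?** Section 11.2 assesses safety by application-site tolerability, adverse events and physical examinations. Section 8.4 records early discontinuation under five general categories, none specific to skin reactions. Section 12.3 plans descriptive summaries, with a possible comparison of patients' responses here and in SD-003. The protocol does not make discontinuation for a skin reaction a primary result, and it states no comparison between centers. No table or conclusion named in the protocol changes if the phrase is reworded.

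**The case for a change.** The best case for acting is that an open list does not wholly repair a bad example. The two examples seem to have been written for a cream applied to a limited area, one covering reactions within it and the other reactions spreading past it. With whole-body use that division collapses. A severe, widespread reaction on treated skin that does not need systemic steroids then matches neither example. An investigator could infer that such a reaction was meant to be excluded, particularly since Section 13 also urges that subjects be kept in the study to completion. In addition, Section 11.4 leaves cream-related skin site changes out of the adverse drug reaction definition and refers them to evaluations in Section 9.3, which describes none. Discontinuation might therefore be one of the few visible signs of local intolerance. Rewording would cost little.

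Part of this stands. The example is badly worded, and its likely origin in a limited-area setting is a fair reading. The inference that treated skin is excluded does not stand, because the introductory words of ground 1, grounds 3 and 4, and Section 8.4 all point the other way. The sentence urging completion is itself made subject to good clinical judgment on safety. The gap in Section 11.4 concerns how skin changes are classified and captured. Rewording an example in Section 13 would not close it, and the adverse event definition in Section 11.4 carries no such exception. Low cost alone does not justify a change that alters no decision and no result.

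**Conclusion.** The mismatch between the first example in Section 13 and the whole-body application in Sections 10.1 and 10.2 is genuine, but it is a clerical slip confined to one illustrative phrase. Ground 1 can still be met, and a severe skin reaction on treated skin can end participation by six routes, each in the investigator's hands. The difference from Section 8.4 is one of degree. A divergence between centers is possible in principle, but nothing in the text shows it, and the protocol plans no analysis that would be affected.

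This rests on two assumptions. Investigators must read the list in ground 1 as open, which is what its introductory words say. The statistical analysis plan, which is not at hand, must define no outcome by this sub-bullet; nothing in the protocol suggests that it would.

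The sponsor and investigators can reconcile the phrase with Sections 10.1 and 10.2 whenever the text is next revised, and the clinical content is theirs to settle. The plan needs no change on this account, because rewording would alter no stopping route, no data collected and no conclusion.

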14. ETHICAL CONDUCT OF THE STUDY

This study will be conducted in accordance with ethical principles founded in the Declaration of Helsinki and in compliance with the protocol, International Conference on Harmonisation [ICH] GCP, and applicable local legal and regulatory requirements (including ICH guidelines, the European Union Clinical Trials Directive 2001/20/EC, the GCP Directive 2005/28/EC, the requirements of local IEC/IRB, and the US Code of Federal Regulations, Title 21 CFR Part 50, 54, 56 and 312).

14.1. Independent Ethics Committee (IEC) and Relevant Authorities

This protocol and the subject informed consent form (ICF) must be reviewed and approved by an institutional review board (IRB)/independent ethics committee (IEC) complying with the requirements of 21 CFR Part 56 and local regulatory requirements before subject enrollment at each site. The letter (or certificate of approval) from the IRB/IEC must be received by the Sponsor or its designee prior to delivery of clinical supplies. The IRB/IEC will be notified of any SAE or suspected unexpected serious adverse reaction in accordance with local regulatory requirements.

Any changes to the study design will be formally documented in protocol amendments and approved by the IRB prior to implementation, except in the case of changes made to protect patient safety, which will be implemented immediately.

Clinical Trial Authorization will be obtained prior to initiation of the study from the U.S. Food and Drug Administration.

14.2. Informed Consent

The principles of informed consent in the Declaration of Helsinki, in ICH Good Clinical Practice and in US 21 CFR Part 50 (Protection of Human Subjects) will be implemented before any protocol-specified procedures or interventions are carried out.

A signed informed consent / assent form (ICF) shall be obtained from each patient and/or legal guardian if under 18 years of age prior to entering the study. The Investigator is responsible for obtaining written informed consent / assent from the patient and or legal guardian after adequate explanation of the aims, methods, anticipated benefits, and potential hazards of the study and before any protocol specific screening procedures or any study medications are administered. Information should be given in both oral and written form whenever possible and deemed appropriate by the IRB. Patients will also be asked to consent to allow the Sponsor, Sponsor representative or external regulatory auditor to review their medical records to confirm compliance with GCP.

The acquisition of informed consent / assent should be documented in the patient's medical record and the ICF should be signed and personally dated by the patient and or legal guardian and by the person who conducted the informed consent / assent discussion (not necessarily by the Investigator). The original signed ICF should be retained in the Investigator Site File and a copy of the signed consent should be provided to the patient prior to participation in the trial.

The patient will be informed that they may withdraw from the study at any time without prejudice to further treatment. They will receive all information that is required by local regulations and ICH guidelines.

15. STUDY AND DATA MANAGEMENT

15.1. Protocol Amendments

No amendments to the protocol will be implemented prior to agreement from the Sponsor, and prior to approval from appropriate authorities.

15.2. Monitoring

The study monitor will review the progress of the study on a regular basis to ensure adequate and accurate data collections. Monitoring site visits to review eCRFs, patient case notes, and administrative documentation including the Investigator Site File and frequent telephone communications with site will be performed throughout the study.

At each study monitoring visit the Investigator will make available all records pertaining to the study. To allow sufficient time to assemble documentation for the study monitor, monitoring visits will be confirmed in advance of planned visits.

All communications, between the Sponsor, designated study representative, and Investigator should be documented for the study file.

15.3. Quality Assurance

To ensure compliance with GCP and all applicable regulatory requirements, the investigator[s]/institution[s] will permit study-related audits, IRB/IEC review, and regulatory inspection[s], providing direct access to source data/documents.

The Sponsor or Sponsor representative or external regulatory agency may at any time during or after completion of the study conduct a Good Clinical Practice (GCP) audit.

Prior notice will be given to each site selected for audit in advance of a planned GCP audit.

15.4. Data Recording

The Investigator has the responsibility for ensuring that all source documents (i.e., study and/or medical records) are completed and maintained according to the study protocol, and are available at the site.

15.5. Data to be Considered as Source Data

The following are considered source data: Informed consents, laboratory reports, patient files, and IMP accountability list.

The following information must be entered in the patient's file:

- Patient's name, address and date of birth
- Subject's weight, height, and temperature
- Medical history
- Concomitant medication

- Unambiguous reference to the clinical study (clinical study number, screening number and patient number)
- Information on main selection criteria (diagnosis)
- Dates of study drug administration, and tube count of study drug obtained at each visit indicated
- Date of informed consent / assent
- Physical examinations and results done at the appropriate visits
- Dates and time of urine pregnancy test
- Did AE(s) occur, improve or worsen?
- Date of discontinuation / completion of the clinical study
- For subjects that are lost to follow-up, the site is to document attempts made to contact the subject *i.e., telephone, email, certified letter*

All other data recorded directly in the eCRF [*i.e., no prior written or electronic record of data*] will be considered as source data.

15.6. Confidentiality

The Investigator must assure that the patients' anonymity will be maintained. On all study documentation, with the exception of the consent form and patient ID logs, patients will only be identified by their unique identification code and initials and will not be referred to by name.

15.7. Retention of Study Data

The Investigator is required to maintain all study documentation, including regulatory documents, copies of eCRFs, signed informed consent forms, and records for the receipt and disposition of study medications, for a period of two years following approval date of a New Drug Application for the drug, or until 15 years after completion of the study, whichever is later.

During the study, the Investigator must make study data accessible to the Sponsor, IRB and the Food and Drug Administration. A file for each patient must be maintained that includes the signed informed consent / assent form and copies of all source documentation related to that patient. The Investigator must ensure the availability of source documents from which the information on the eCRF was derived.

15.8. Communication and Publication of Results

The results of the study will be presented in an integrated Clinical Study Report according to GCP.

The results from the study will be presented to the principal investigators when the statistical analyses have been completed. On the basis of these data, the CRO in cooperation with the sponsor, will write and report on the trial.

A summary of the Clinical Study Report will be sent to the regulatory authorities and to the IRB after termination of the study.

[figure not shown]
The Clinical Study Report shall form the basis for a manuscript intended for publication in an international, scientific journal at a suitable time agreed to by the Sponsor.

No data from the study will be published, presented, or communicated without the mutual agreement of the Sponsor.

17. APPENDICES

17.1. Appendix 1 EB Subtypes

Clinical Features of EB

Epidermolysis Bullosa Simplex (EBS)

EBS Subtypes	Features
Weber-Cockayne	
• Most common and localized form of EBS.• Blisters develop on hands and feet in response to friction.• Usually presents in infancy as child is starting to crawl and walk.• Lesions heal without scarring but there may be thickening of the skin on soles and palms.
Koebner	
• Generalized EBS where blisters develop all over the body but commonly on hands, feet and extremities.• Presents at birth or early in infancy.• May be mild involvement of mucous membranes and nails.• Thickening of skin and plaques develop on palms and soles.
Dowling-Meara	
• Generalized and severe form of EBS.• Presents at birth with blistering on the face, trunk and limbs.• Thickened skin may cause calluses that limit or interfere with joint movement.• Nails often affected.• May involve other organs including inside the mouth, gastrointestinal and respiratory tract.• Widespread involvement may cause death in infancy but usually there is significant improvement with age.
EB with muscular dystrophy	
• Due to plectin mutation.• Variable degree of blistering followed later in life by muscular dystrophy.• Muscular dystrophy does not arise in all cases with plectin mutation.

Recessive Dystrophic Epidermolysis Bullosa (RDEB)

DEB Subtypes	Features
Recessive DEB	
• May present with severe blistering (Hallopeau-Siemens) or mild disease (non-Hallopeau-Siemens).• Generalized severe blistering is more common and involves large areas of skin and mucous membranes.• Blisters heal but with scarring and deformity causing limited movement as fingers and toes may be fused together (mitten hands).• Complications such as infection, malnutrition and dehydration may cause death in infancy and those that survive are at great risk of developing squamous cell carcinoma.• Milia (small white cysts) are often present at healed but scarred sites.

Junctional Epidermolysis Bullosa (JEB)

JEB Subtypes	Features
Non-Herlitz JEB	
• Generalized blistering and mucosal involvement present at birth or soon after.• Scalp, nails and teeth involved.• Often sparse hair.• Complications such as infection, malnutrition and dehydration may cause death in infancy but many survive.
